16 PUBLICATION OF TRIAL RESULTS

Data from the study will be published in an international peer-reviewed journal. Order of the authors will be agreed based on the contribution of each author in the definition, executing and writing stages.

17 FINANCIAL CONDITIONS

This study is initiated by Onxeo (formerly known as BioAlliance Pharma).

The study drug will be provided to participants at no cost. Patient will not be reimbursed for participation in this study. Actual reasonable travel reimbursement assistance may be available if needed after agreement of the sponsor.

This research is funded by Onxeo (formerly known as BioAlliance Pharma). The researchers do not, however, hold a direct financial interest in the sponsor or in the outcome of the study.

19 LIST OF APPENDICES

Appendix I: HCC staging according to BCLC

Appendix II: Child-Pugh score

Appendix III: CLIP and MELD scores

Appendix IV: ECOG performance status

Appendix V : NHYA classification

Appendix VI: DT protocol of reconstitution

Appendix VII: Pharmacokinetic protocol

Appendix VIII: Biomarkers protocol

[figure not shown]
Appendix IX: RECIST 1.1 and mRECIST criteria

Appendix X: NCI CTC AE v4.0 classification

Appendix XI : List of inhibitors and inducers of CYP3A4, CYP2D6 and P-gp

Appendix XII : EQ- 5D™ Questionnaire

I. BCLC proposal for HCC staging

Barcelona Clinic Liver Cancer (BCLC) classification in HCC (adapted from EASL-EORTC Clinical Practice Guidelines: Management of hepatocellular carcinoma, J. Hepatol 2012)

II. Child-Pugh score

	1 point	2 points	3 points
Encephalopathy	Absent	Asterixis	Confusion
Ascites	Absent	Mild/Moderate	Severe/Refractory
Albumin	> 35g/L	35-28g/L	< 28g/L
Total bilirubin	< 35µM/L ≤ 2mg/dl	35-50µM/L 2-3 mg/dl	> 50µM/L >3 mg/dl
Prothrombin time rate (INR)	> 50% (< 1.7)	40-50% (1.7-2.3)	< 40% (> 2.3)

Class A: 5-6 points

Class B: 7-9 points

Class C: 10-15 points

III. CLIP Score and MELD score

CLIP Score

	0 point	1 point	2 points
Child-Pugh	A	B	C
Tumour morphology	Uninodular extension ≤ 50%	Multinodular extension ≤ 50%	Massive or extension > 50%
AFP	< 400	≥ 400	
Portal vein thrombosis	No	Yes	

Clip Score = 0

Clip Score = 1

Clip Score = 2

Clip Score = 3

Clip Score = 4 to 6

MELD Score

MELD (Model for End-stage Liver Disease) score is calculated according to the formula below:

$$\text{MELD} = 9.57 * \text{Log creatinine (mg/dl)} + 3.78 * \text{Log bilirubin (mg/dl)} + 11.2 * \text{Log INR} + 6.43$$

IV. ECOG Performance Status

Grade	ECOG
0	Fully active, able to carry on all pre-disease performance without restriction
1	Restricted in physically strenuous activity but ambulatory and able to carry out work of a light or sedentary nature, (eg, light house work, office work)
2	Ambulatory and capable of all selfcare but unable to carry out any work activities. Up and about more than 50% of waking hours
3	Capable of only limited selfcare, confined to bed or chair more than 50% of waking hours
4	Completely disabled. Cannot carry on any selfcare. Totally confined to bed or chair
5	Dead

V. Stages of Heart Failure – NYHA Classification

The New York Heart Association (NYHA) functional classification system relates symptoms to everyday activities and the patient's quality of life:

Class	Patient Symptoms
Class I (Mild)	No limitation of physical activity. Ordinary physical activity does not cause undue fatigue, palpitation, or dyspnoea (shortness of breath).
Class II (Mild)	Slight limitation of physical activity. Comfortable at rest, but ordinary physical activity results in fatigue, palpitation, or dyspnoea.
Class III (Moderate)	Marked limitation of physical activity. Comfortable at rest, but less than ordinary activity causes fatigue, palpitation, or dyspnoea.
Class IV (Severe)	Unable to carry out any physical activity without discomfort. Symptoms of cardiac insufficiency at rest. If any physical activity is undertaken, discomfort is increased.

VI. Doxorubicin Transdrug™ protocol of reconstitution

DOXORUBICIN TRANSDRUG™ 10 mg - POWDER FOR SUSPENSION FOR INJECTION PROTOCOL OF RECONSTITUTION AND ADMINISTRATION PROCEDURE

1. DOSAGE FORM

Doxorubicin Transdrug™ 10 mg (DT) is a powder for suspension for injection which contains doxorubicin, an antineoplastic agent as active drug. DT is a [REDACTED] for suspension for intravenous injection, presented in glass vials with a rubber cap and a flip-off seal. Each vial contains 10 mg equivalent doxorubicin and [REDACTED]

2. RECOMMENDATION FOR SAFE HANDLING

The following information is intended for medical and healthcare professionals only. Caution should be exercised in the handling and preparation of DT. The reconstitution must be carried out under a laminar flow, by a suitably trained staff. The vials must never be opened before reconstitution. DT must be injected by strict intravenous route. If any signs or symptoms of extravasation have occurred, the infusion should be immediately stopped and restarted in another vein. The waste disposal must be performed with respect to each centre procedure for genotoxic and cytotoxic compounds.

3. STORAGE

Store in the refrigerator (2°C-8°C).

After reconstitution:

Chemical and physical in-use stability has been demonstrated for 24h following initial reconstitution when stored at refrigerated conditions (2°C-8°C).

All precaution should be taken during the reconstitution in order to avoid any microbiological contamination. In-use storage times and conditions prior to use are the responsibility of the user and should not be longer than 24 hours at 2°C to 8°C.

Do not store partially used vials for future patient use.

4. MATERIAL FOR RECONSTITUTION

- Vent needles dispensing pin
- 5 µm filters (green colour code)
- 1.2 µm filters (blue colour code)
- 30 ml Luer Lock Syringes
- Needles 21G x 1 ½ " (0.8 x 38 mm)
- 250 ml sterile bag for injectable solution
- 2.5% sterile glucose solution for injection

5. RECONSTITUTION AND FILTRATION (*Hospital Pharmacy, under laminar flow*)

It is important to read the entire content of this section prior to the preparation of this medicinal product.

Aseptic technique must be strictly observed throughout handling of DT since no preservative is present.

Caution should be exercised in the handling and preparation of DT. The use of gloves is required.

The preparation for intravenous infusion of DT is performed according to two main steps (reconstitution and filtration) as described hereafter.

Step 1 – Reconstitution of DT powder

- Calculate the dose of DT and determine the number of vials needed, based upon the recommended dose and the patient's body surface area (BSA), according to the tables below.
- Get the vials for reconstitution out of the refrigerator.
- Keep the vials for reconstitution at room temperature for at least 30 min before reconstitution.
- Reconstitute each vial containing HCl Doxorubicin 10 mg with 25 mL of 2.5% glucose as follows :
 - Remove the flip-off seal of each vial.
 - Insert a vent needle through the rubber cap.
 - Open the vent needle protective cap.
 - Add 25 ml of sterile glucose 2.5% for injection using a 30 ml syringe to each DT vial, to yield a suspension containing 0.4 mg/ml of doxorubicin HCl. The addition of glucose may induce the formation of a foam;
 - Close the vent needle and shake each vial for a minimum of 10 seconds to completely disperse the DT. Visually inspect the vial for particulate matter and continue shaking until complete dispersion is obtained. Once reconstituted the resulted nanoparticle suspension for infusion of DT is a red-orange homogeneous suspension.

Step 2 - Double filtration of the DT suspension through 5 µm filter and 1.2 µm filter into a sterile bag

Each individual vial has to be filtered using one unique set of 5 µm and 1.2 µm filters and 30 mL syringe.

- Carefully open the protective cap of the vent needle.
- Withdraw the suspension of DT into a sterile 30 mL syringe. During the collection of reconstituted suspensions, pay attention to avoid the aspiration of the foam in the syringe
- Remove the 30mL syringe with the suspension of DT.
- Adapt on each 30 mL syringe containing the suspension of DT and in series according the following sequence :
 - one 5 µm filter provided (green colour code),
 - one 1.2 µm filter provided (blue colour code) and then,

- the sterile bag provided.
- Instill the suspension of each syringe into the sterile bag.
- Operate as above to reconstitute other vials intended for the preparation in order to obtain in the sterile bag the appropriate volume of DT 0.4 mg/mL as determined previously.
- The total suspension of DT corresponding to the appropriate volume for the patient will be administered to the patient without any further dilution.
- Stick the label onto the bag and store it in a refrigerator at 2°C to 8°C.
- If not used immediately, in-use storage times and conditions prior to use are the responsibility of the user and should not be more than 24 hours following preparation and should be stored at 2°C to 8°C.
- Discard any unused portion of suspension of DT.
- Do not further dilute the reconstituted suspension of DT.

6. ADMINISTRATION TO THE PATIENT

1. Day 0 – Oral premedication the Day before study treatment administration

- The day before DT injection, patient will receive a premedication with methylprednisolone 32 mg p.o. (or equivalent) + cetirizine 20 mg p.o (or equivalent)

2. Day 1 – Study treatment administration

- Get the suspension bag out of the refrigerator and leave it at room temperature for at least 30 min;
- One hour before DT administration (H-1), patient will receive premedication with methylprednisolone 32 mg p.o. (or equivalent) and cetirizine 20 mg p.o (or equivalent);
- Then, the suspension of DT will be infused over 6 hours through intravenous route using an infusion pump or a syringe-pump in order to insure a constant flow;
- Patient will have a continuous SaO₂ monitoring during infusion and then 24 hours after the infusion starts;
- The duration of infusion must be increased (flow reduced by half) in case of occurrence of pulmonary toxicity (cf section 7.6: Urgent Safety Measures). Any modification in the infusion rate must be recorded in the e-CRF;
- Fasting is not needed.

3. Day 2 – Oral premedication the Day after study treatment administration

- The Day after DT administration (D2), patient will receive a premedication with methylprednisolone 32 mg p.o. (or equivalent) and cetirizine 20 mg p.o (or equivalent);

DT dosing table and volume to be administered at a dose of 20 mg/m² according to patient's body surface area

DOXORUBICIN TRANSDRUG™ - DOSE = 20 mg/m²									
Body surface area*	1.5 m²	1.6 m²	1.7 m²	1.8 m²	1.9 m²	2.0 m²	2.1 m²	2.2 m²	2.3 m²
Total dose per patient	30 mg	32 mg	34 mg	36 mg	38 mg	40 mg	42 mg	44 mg	46 mg
Number of vials (10 mg/vial) to reconstitute**	3	4	4	4	4	4	5	5	5
Final volume of suspension obtained to be administered (0.4 mg/mL)	75 ml	80 ml	85 ml	90 ml	95 ml	100 ml	105 ml	110 ml	115 ml

DT dosing table and volume to be administered at a dose of 30 mg/m² according to patient's body surface area

DOXORUBICIN TRANSDRUG™ - DOSE = 30 mg/m²									
Body surface area*	1.5 m²	1.6 m²	1.7 m²	1.8 m²	1.9 m²	2.0 m²	2.1 m²	2.2 m²	2.3 m²
Total dose per patient	45 mg	48 mg	51 mg	54 mg	57 mg	60 mg	63 mg	66 mg	69 mg
Number of vials (10 mg/vial) to reconstitute**	5	5	6	6	6	6	7	7	7
Final volume suspension obtained to be administered (0.4 mg/mL)	112.5 ml	120 ml	127.5 ml	135 ml	142.5 ml	150 ml	157.5 ml	165 ml	172.5 ml

DT dosing table and volume to be administered at a dose of 15 mg/m² according to patient's body surface area

DOXORUBICIN TRANSDRUG™ - DOSE = 15 mg/m²									
Body surface area*	1.5 m²	1.6 m²	1.7 m²	1.8 m²	1.9 m²	2.0 m²	2.1 m²	2.2 m²	2.3 m²
Total dose per patient	22.5 mg	24 mg	25.5 mg	27 mg	28.5 mg	30 mg	31.5 mg	33 mg	34.5 mg
Number of vials (10 mg/vial) to reconstitute**	3	3	3	3	3	4	4	4	4
Final volume suspension obtained to be administered (0.4 mg/mL)	56.5ml	60 ml	64 ml	67.5 ml	71.5 ml	75 ml	79 ml	82.5 ml	86.5 ml

* Round off the Body surface area in the following way:

From 1.50 to 1.54 m², round down to 1.5 m²

From 1.55 to 1.59 m², round up to 1.6 m²

**The number of vials to reconstitute could be over if the volume of suspension collected is not sufficient.

VII. Pharmacokinetic protocol

During the previous HCC studies, preliminary pharmacokinetic parameters were evaluated and individual pharmacokinetic profiles have been determined. The data obtained pointed out a wide inter-individual variability, which require evaluation of the pharmacokinetic profile in patients with HCC.

In this study, patients will be treated with doses at 20 or 30 mg/m² of Doxorubicin Transdrug™, repeated every 4 weeks until progression of the disease or unacceptable toxicity.

The aim of pharmacokinetic evaluation is first, to determine the population pharmacokinetic parameters. Secondly, the objective is to analyse the pharmacokinetic / pharmacodynamic correlation with DT efficacy and toxicity, and to evaluate inter-Cycles AUC stability.

Due to its specific formulation (), late exposure (>48 hours after DT infusion) has to be evaluated in order to be able to characterize the pharmacokinetic profile of doxorubicin and doxorubicinol.

For this purpose, blood sampling will be performed at the first and third treatment Cycles. For patients still on study treatment after Cycle 3, an optional and limited pharmacokinetic blood sampling will be done at Cycle 4, Cycle 6 (e.g. every 2 cycles until the end of study treatment). Blood collection (10mL/sample) will have to be taken from a peripheral vein. DT will be infused at D1 of each cycle over 6 hours through intravenous route.

At Cycle 1 and Cycle 3:

Blood samples will be collected at the following times on D1, D2, D3, D4, D8, D14 and D28 during the 1st and the 3rd Cycle of DT treatment, to perform total and free doxorubicin and doxorubicinol assays.

D1 (D1= DT administration) (in patient)											D2 (in patient)	
T0	T30min	T60min	T2h	T4h	T6h	T6h30	T7h	T7h30	T8h	T12h ± 2h	T24h ± 2h	T33h ± 2h
Before infusion	30min after start of infusion	60min after start of infusion	2h after start of infusion	4h after start of infusion	3 to 5 min before the end of infusion	30min after end of infusion	1h after end of infusion	1h30 after end of infusion	2h after end of infusion	6h ± 2 hours after end of infusion	24h ± 2 hours after start of infusion	33h ± 2 hours after start of infusion

- D1: T₀: before the beginning of treatment injection,
- D1: T_{30min}, T_{60min}, T_{2h}, T_{4h} after start of the infusion, T_{6h} (3-5 min before the end of infusion), then T_{6h30min} (30 min after the end of infusion), T_{7h} (1 hour after the end of infusion), T_{7h30} (1 hour 30 after the end of infusion), T_{8h} (2 hours after the end of infusion) and T_{12h ± 2h} (6 ± 2 hours after the end of infusion)
- D2: T_{24h} and T_{33h} (24 ± 2 hours and 33 ± 2 hours after start of infusion); The time H_{33h} has been taken in order to avoid blood sampling during night

- Then D3: T_{48h} (48 ± 2 hours after start of infusion), D4: T_{72h} (72 ± 2 hours after start of infusion), D8, D14 and D28 after DT administration.

D3 (in or outpatient)	D4 (in or outpatient)	D8 (outpatient)	D14 (outpatient)	D28 (in or outpatient)
T _{48h ± 2h}	T _{72h ± 2h}	T _{7days}	T _{13days}	T _{27days}
48h ± 2 hours after start of infusion	72h ± 2 hours after start of infusion	7 days after infusion (morning or afternoon)	13 days after infusion (morning or afternoon)	27 days after infusion (morning or afternoon)

At Cycle 4, Cycle 6, then every 2 cycles until the end of study treatment (optional):

D1 (D1= DT administration) (in patient)				D14 (outpatient)	D28 (in or outpatient)
T0	T4h	T6h	T8h	T13days	T27days
Before infusion	4h after start of infusion	3 to 5 min before the end of infusion	2h after end of infusion	13 days after infusion (morning or afternoon)	27 days after infusion (morning or afternoon)

Blood Sampling procedures:

The blood will be taken in 10 ml EDTA tubes. Blood samples will be immediately put into a glass of ice + water after sampling. Then, **centrifugation will be performed immediately at 3000 rpm, at +4°C ± 2°C for 20 min, to separate out the plasma.**

The plasma will then **be divided into 2 polypropylene cryotubes, each of which must contain at least 1.5ml of plasma, and then immediately frozen at -80°C; Plasma can be alternatively kept at -20°C if -80°C is not feasible.**

The samples may be centrifuged **individually**, after the sample is collected.

Each sample shall be identified as follows, using a label that is resistant to the storage temperature of -80°C:

- the protocol number BA2011/03/04,
- the centre number,
- the identification number of the patient,
- the theoretical sampling time,
- the date of sampling.

A check-list will be kept, including the exact identification of each sample and the real sampling times.

Onxeo (formerly known as BioAlliance Pharma) will ensure dispatching of samples to third parties in charge of doxorubicin and its metabolite dosage. Study samples will be transferred

periodically to the laboratory in charge of these dosages using a container filled with enough dry ice to ensure that samples will be kept deep frozen at about -80°C.

VIII. Biomarkers protocol

The blood will be taken in a 10 ml K2EDTA tube. Immediately gently invert the tube 10 times, and store it at room temperature until centrifugation.

Aliquoting and freezing should be completed within 60 min of specimen collection.

1. **Set the centrifuge at 6°C.** Plasma is obtained by centrifugating the blood sample in a swing **centrifuge at the speed =1300 g for 10 min** under refrigerated conditions (2-6°C).
 - a. NOTE: Ensure rotor is balanced.

2. Using a pipette the resultant plasma is transferred (but not the white cells in the buffy coat) to a **15 ml conical** bottom Falcon® tube.
 - **Centrifuge the second plasma tube at 2400 g or rpm for 15 min** under **refrigerated conditions (2-6° C)** to remove all potentially remaining cellular material.

 - Save the “buffy coat” containing white cells and the red blood cells (RBC), separately as a source of DNA. Using a pipette, transfer buffy coat aliquots and red blood cell aliquots into **labelled 1.8 ml cryovials and freeze them at -70°C to -80°C.**

3. Transfer the resultant plasma after second centrifugation, into a new **15 mL conical bottom Falcon® tube**, using a pipette. Pipette to approximately 10% from the bottom of the tube to ensure no cellular material is collected.

The purpose of double spinning the plasma is to remove all cellular contaminants so that the plasma is suitable for plasma DNA analysis. It is extremely important, therefore, not to disturb the buffy coat after the first spin, and any pellet after the second spin.

4. Gently mix the plasma and transfer 800-1000 µl aliquots into labeled **1.8 ml cryovials**, without delay. Freeze the cryovials **at -70°C to -80°C.**

IX. RECIST1.1 and mRECIST Criteria (Lencioni and Llovet 2010^[53])

Tumour response and progression will be assessed by CT scan or MRI according to Response Evaluation Criteria In Solid Tumors (RECIST) guideline version 1.1 and modified RECIST Criteria for HCC (Eisenhauer 2009^[54]).

RECIST 1.1 Criteria

Target lesions: the number of lesions to select as target lesions is a maximum of 2 lesions per organ and 5 lesions in total. Target lesions should be selected on the basis of their size (those with the longest diameter) and their suitability for accurate repeated measurements.

At baseline, the sum of the diameters: longest diameters (LD) for extra nodal target lesions and short axis diameters (SAD) for nodal lesions will be calculated and reported as the baseline sum LD. This baseline sum LD will be used as the reference by which to characterize the objective tumour response.

Non target lesions: all other lesions should be identified as non-target lesions and should be recorded at baseline. Measurements of these lesions are not required, but the presence or absence of each should be noted throughout the study.

RECIST 1.1 response criteria used to determine the response on target lesions:

Evaluation of target lesions

Complete Response (CR):	Disappearance of all targets extra nodal lesions and the regression of all nodal lesions to < 10 mm SAD.
Partial Response (PR):	At least a 30% decrease in the sum of diameters of target lesions, taking as reference the baseline sum diameters
Progressive Disease (PD):	At least a 20% increase in the sum of diameters of target lesions, taking as reference the smallest sum on study (this includes the baseline if that is the smallest on study) . In addition to the relative increase of 20%, the sum must also demonstrate an absolute increase of at least 5 mm. The appearance of one or more new lesions is considered progression.
Stable Disease (SD):	Neither sufficient shrinkage to qualify for PR nor sufficient increase to qualify for PD, taking as reference the smallest sum of diameters while on study.

Evaluation of non-target lesions

Complete Response (CR):	Disappearance of all non-target lesions and normalization of tumour marker level. All lymph nodes must be non pathological in size (< 10 mm short axis)
-------------------------	---

Non-CR/Non-PD::	Persistence of one or more non-target lesion(s) and/or maintenance of tumour marker level above the normal limits
Progressive Disease (PD):	Unequivocal progression of existing non-target lesions and/or appearance of one or more new lesions *

**Although a clear progression of “non target” lesions only is exceptional, in such circumstances, the opinion of the treating physician should prevail and the progression status should be confirmed later on by the review panel (or study chair).*

Evaluation of overall response (RECIST 1.1)

Target lesions	Non-target lesions	New lesions	Overall response
CR	CR	No	CR
CR	Incomplete response/SD	No	PR
PR	Non-PD	No	PR
SD	Non-PD	No	SD
PD	Any	Yes or No	PD
Any	PD	Yes or No	PD
Any	Any	Yes	PD

Modified RECIST:

Modified RECIST (mRECIST) criteria are considered as the best criteria to evaluate the efficacy of treatment of HCC. mRECIST criteria are endorsed by EASL and AASLD societies and recently by the FDA (Lencioni and Llovet, 2010). The definitions used in the mRECIST are described below:

Target lesions: the lesion should be located in the LIVER:

- Be classified as a RECIST measurable lesion (in at least one dimension as 1 cm or more);
- Be suitable for repeat measurement;
- Show intratumoural arterial enhancement on contrast-enhanced CT or MRI.

mRECIST response criteria used to determine the response on target lesions:

- **Complete response (CR)** = Disappearance of any intratumoural arterial enhancement in all target lesions;

- **Partial response (PR)** = At least a 30% decrease in the sum of diameters of viable (enhancement in the arterial phase) target lesions taking as reference the baseline sum of the diameters of target lesions;
- **Progressive Disease (PD)** = An increase of at least 20% in the sum of the diameters of viable (enhancing) target lesions, taking as reference the smallest sum of the diameters of viable (enhancing) target lesions recorded since treatment started;
- **Stable Disease (SD)** = Any cases that do not qualify for either partial response or progressive disease.

Note: Infiltrative-type HCC should be defined as non target lesion when the mass shows ill-defined, not suitable for repeat measurements. The same applies for HCC lesions previously treated with local or systemic treatments. They may or not be considered as target lesions according to delineation and suitability for repeat measurements.

mRECIST response criteria used to determine the response on non target lesions are the same as RECIST 1.1 response criteria. However, as for target lesions, tumour necrosis should be taken into account when assessing the response to nontarget lesions. The disappearance of any intratumoural arterial enhancement in nontarget lesions should be considered equivalent to the disappearance of nontarget lesions. Likewise, the persistence of intratumoural arterial enhancement in one or more nontarget lesions should be considered equivalent to the persistence of one or more nontarget lesions and therefore declared incomplete response/stable disease.

Special recommendations can be made:

- Portal vein thrombosis should be considered a non measurable lesion due to the difficulty in performing consistent measurements of the malignant thrombus during the course of the treatment;
- Porta hepatis lymph node can be considered as malignant if the lymph node axis is at least 20 mm;
- Pleural effusion or ascites: cytopathologic confirmation of the neoplastic nature of any effusion that appears or worsens during treatment is required when the measurable tumour has met criteria for response or stable disease (peritoneal carcinomatosis is a rare event in HCC).

New lesions are:

- A newly detected hepatic nodule is classified as HCC when its longest diameter is at least 1 cm and the nodule shows the typical vascular pattern of HCC on dynamic imaging (hypervascularisation in the arterial phase with washout in the venous or late venous phase);
- Liver lesions larger than 1 cm without typical vascular pattern with evidence of at least 1 cm interval growth in subsequent scans;

- Individual radiological event will be adjudicated in retrospect as progression at the time it was 1st detected by imaging techniques even if strict criteria were fulfilled only on subsequent radiological testings.

Overall tumoural response takes into account all possible combinations of tumoural responses on target and non target lesions. The guidelines for the evaluation of overall response are similar using RECIST 1.1 or mRECIST for HCC and as shown in table below.

Evaluation of overall response (mRECIST for HCC)

Target lesions	Non-target lesions	New lesions	Overall response
CR	CR	No	CR
CR	Incomplete response/SD	No	PR
PR	Non-PD	No	PR
SD	Non-PD	No	SD
PD	Any	Yes or No	PD
Any	PD	Yes or No	PD
Any	Any	Yes	PD

X. NCI CTC classification

The NCI Common Terminology Criteria for Adverse Events version 4.0 is located on the internet at the following URL:

http://evs.nci.nih.gov/ftp1/CTCAE/CTCAE_4.03_2010-06-14_QuickReference_8.5x11.pdf

XI. List of inhibitors and inducers of CYP3A4, CYP2D6 or P-gp

Non exhaustive list adapted from FDA recommendations on Drug development and Drug Interactions: table of substrates, inhibitors and inducers:

<http://www.fda.gov/drugs/developmentapprovalprocess/developmentresources/druginteractionslabeling/ucm093664.htm>

Enzyme	Inhibitor		Inducer		
	Class	DCI	Class	DCI	
CYP3A4	Antifungal drugs	ketoconazole	itraconazole	Antibiotics	rifampin
		posaconazole	voriconazole		nafcillin
		fluconazole			
	Antibiotics	clarithromycin	telithromycin	Antiepileptic drugs	carbamazepine
		erythromycin	ciprofloxacin		phenytoin
		isoniazid			rufinamide
	Antiviral drugs	boceprevir	telaprevir	Antiviral drugs	efavirenz
		ritonavir	saquinavir		etravirine
		indinavir	lopinavir/ritonavir	Others	amprenavir
ritonavir		nelfinavir	modafinil		
amprenavir		atazanavir	armodafinil		
darunavir/ritonavir		fosamprenavir	prednisone		
tipranavir/ritonavir			bosentan		
Calcium channel blockers	mibefradil	diltaziem	aprepitant		
	verapamil	amlodipine	pioglitazone		
Antiarrytmics	amiodarone	ranozaline	echinacea		
Antidepressant/Anxiolytic	nefazodone	alprozolam			
	fluoxetine	fluvoxamine			
Others	cimetidine	ranitidine			

		aprepitant cyclosporine bicalutamide imatinib grapefruit juice goldenseal	atorvastatin oral contraceptives cilostazol nilotinib ginkgo		
Enzyme	Inhibitor		Inducer		
CYP2D6	Antiarrhythmics	quinidine propafenone	amiodarone	none known	
	Calcium channel blockers	diltaziem	verapamil		
	Antidepressant	fluoxetine paroxetine desvenlafaxine sertraline	bupropion duloxetine escitalopram		
	Antifungal drugs	terbinafine			
	Antibiotics	telithromycin			
	Antiviral drugs	ritonavir			
	Others	methadone cimetidine oral contraceptives cinacalcet hydroxychloroquine gefitinib hydralazine	diphenhydramine ranitidine febuxostat celecoxib imatinib echinacea		
P-gp	Antifungal drugs	itraconazole	ketoconazole	Antibiotics	rifampin
	Antibiotics	azithromycin erythromycin	clarithromycin	Antiepileptic drugs	carbamazepine phenytoin
	Antiviral drugs	lopinavir	ritonavir	Antiviral drugs	tipranavir/ritonavir

	Antiarrhythmics	amiodarone carvedilol	dronedarone quinidine		
	Calcium channel blockers	diltaziem verapamil	felodipine		
	Others	captopril cyclosporine quercetin	ranolazine conivaptan		

XII. EQ- 5D™ Questionnaire

By placing a tick in one box in each group below, please indicate which statements best describe your own health state today.

Mobility

I have no problems in walking about

I have some problems in walking about

I am confined to bed

Self-Care

I have no problems with self-care

I have some problems washing or dressing myself

I am unable to wash or dress myself

Usual Activities (e.g. work, study, housework, family or leisure activities)

I have no problems with performing my usual activities

I have some problems with performing my usual activities

I am unable to perform my usual activities

Pain/Discomfort

I have no pain or discomfort

I have moderate pain or discomfort

I have extreme pain or discomfort

Anxiety/Depression

I am not anxious or depressed

I am moderately anxious or depressed

I am extremely anxious or depressed

To help people say how good or bad a health state is, we have drawn a scale (rather like a thermometer) on which the best state you can imagine is marked 100 and the worst state you can imagine is marked 0.

We would like you to indicate on this scale how good or bad your own health is today, in your opinion. Please do this by drawing a line from the box below to whichever point on the scale indicates how good or bad your health state is today.

**Your own
health state
today**

SAMPLE

Best
imaginable
health state

100

90

80

70

60

50

40

30

20

10

0

0

Worst
imaginable
health state

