3 TRIAL DESIGN

This is a multicentre, open-label, randomised, comparative, 3 arms (DT 20 mg/m², DT 30 mg/m², Best Standard of Care) study in patients suffering from hepatocellular carcinoma.

The study will be carried out at multiple hepatology or oncology centres that manage patients with HCC with or without cirrhosis. Approximately 100 centres will be involved in the trial.

Based on the survival data obtained in the phase II clinical trial, it has been calculated that 390 patients have to be included to adequately compare the efficacy of DT 20 mg/m² and DT 30 mg/m² to that of BSC.

A safety evaluation will be carried out on a regular basis at least twice a year by the Data Safety Monitoring Board (DSMB) and every 75 patients (around 25 patients/group) whichever comes first.

Patients who meet the inclusion/exclusion criteria will be randomised according to a 1:1:1 ratio to receive either DT 20 mg/m², DT 30 mg/m², or BSC. Only those patients whose survival expectations is longer than 2 months and could receive more than 1 DT infusion will be enrolled.

The study duration for each patient includes a screening period of 28 +/- 2 days maximum before baseline visit (D0 Cycle 1). The patient will then be randomised to receive either DT 20 mg/m² or DT 30 mg/m² as protracted IV infusion over 6 hours once every 4 weeks or BSC.

Patients will receive study therapy until unequivocal tumour progression (assessed by the investigator) or occurrence of unacceptable toxicity.

All patients will be evaluated by CT scan or MRI every 2 months for tumour assessments.

After study therapy discontinuation, an end of study visit will be performed 1 month +/- 7 days after the last DT infusion or last BSC treatment.

Then, a follow up of all patients (including those who withdrew prematurely from the study) will be maintained every 3 months until death. The following information will be recorded:

- Survival (patient alive or deceased)
- Date of progression (in the case of withdrawal for other reason than progression during the study treatment period)
- Administration of any other anti-cancer treatment.

The follow-up period is defined as “until 2 years after Last Patient In”.

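### Appendix VIII gives the second plasma spin as 2400 in either g or rpm, so compliant sites can process biomarker plasma at clearly different forces

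*Combined protocol and SAP*

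**What the plan says.** Appendix VIII (Biomarkers protocol) describes a double spin.

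- **Step 1** runs the whole blood in a swing "centrifuge at the speed =1300 g for 10 min". The unit is g and nothing else.
- **Step 2** moves the plasma, without the buffy coat, to a second tube and instructs: "Centrifuge the second plasma tube at 2400 g or rpm for 15 min". The stated aim is "to remove all potentially remaining cellular material". Buffy coat and red cells are kept separately as a source of DNA.
- **Step 3** moves the plasma to a third tube and adds a safeguard: "Pipette to approximately 10% from the bottom of the tube to ensure no cellular material is collected".

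The appendix explains why this matters: "The purpose of double spinning the plasma is to remove all cellular contaminants so that the plasma is suitable for plasma DNA analysis". It gives no rotor radius, no conversion and no instruction to record the force used.

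Section 7.3.2 plans one additional blood sample for this work, in patients who signed a separate genetic consent, with biomarkers measured before treatment. The synopsis lists blood biomarkers within a secondary objective and within an endpoint. Section 3 says: "Approximately 100 centres will be involved in the trial".

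**The concern.** The step offers g and rpm as alternatives at the same number. The force produced by a given speed depends on the rotor, so the two options are different treatments of the sample. A site that picks either one is compliant, and routine monitoring against the protocol would have no reason to notice.

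What is at stake is whether the banked plasma is comparable across sites. If some sites spin much more gently, more cells may stay in their plasma, and DNA from those cells could mix with the plasma DNA that is to be measured. The difference would follow the site, and so could appear as a site effect in analyses of predictive factors. With one planned baseline sample per patient, a poorly prepared sample has no planned replacement.

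**Working it through.** The plan's figures here are settings, so there is no derived figure to reproduce. The check is a unit conversion.

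**Inputs from Appendix VIII:** first spin 1300 g for 10 min; second spin 2400, in g or rpm, for 15 min.

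**Assumed input:** rotor radius r, which the documents do not give. It is shown over 10 to 25 cm.

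**Formula:** force in multiples of g = (2π × rpm / 60)² × r / 9.80665 with r in metres, or about 1.118 × 10⁻⁵ × r(cm) × rpm². At 2400 rpm this is about 64.4 g per cm of radius.

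| r (cm) | Force at 2400 rpm | Share of 2400 g | Ratio to 1300 g | Force × 15 min (g-min) | rpm needed for 2400 g |
|---|---|---|---|---|---|
| 10 | 644 g | 27% | 0.50 | 9,700 | 4633 |
| 15 | 966 g | 40% | 0.74 | 14,500 | 3783 |
| 20 | 1288 g | 54% | 0.99 | 19,300 | 3276 |
| 25 | 1610 g | 67% | 1.24 | 24,200 | 2930 |

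**Where the readings meet or cross**

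- 2400 rpm equals 2400 g at r = 2400 / 64.4 = about 37.3 cm.
- 2400 rpm equals the first spin's 1300 g at r = 1300 / 64.4 = about 20.2 cm. It is weaker below that radius and stronger above it.
- The first spin delivers 1300 × 10 = 13,000 g-min. The rpm reading matches that at r = 13,000 / (15 × 64.4) = about 13.5 cm, and exceeds it for larger rotors.

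**Spread between compliant sites:** 2400 / 1610 = 1.5-fold at 25 cm, up to 2400 / 644 = 3.7-fold at 10 cm.

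**With the unit fixed at g:** the second spin is 2400 / 1300 = 1.85 times the first at any radius.

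**The case against.** The best defence is that this is a slip in a laboratory appendix, and that the procedure is otherwise built to protect the plasma. The second spin is longer (15 against 10 min), it acts on plasma already drawn off the buffy coat, and the bottom tenth of the tube is left behind. A sensible technician might also read the step as 2400 g or whatever speed delivers it. These points lower the risk. They do not make the two settings equal, and the charitable reading is not what the text says.

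Five stronger readings are tempting, and the documents do not support them:

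- **That every site using rpm spins more weakly than in step 1.** This holds only for radii under about 20.2 cm, and no radius is given.
- **That cells are left in the plasma.** The documents contain no residual-cell data and no minimum clearing force. Incomplete clearance is a risk only.
- **That the damage cannot be dealt with later.** The plasma itself may not reveal the setting, but sites can be asked which setting and rotor they used.
- **That the trial's main results are touched.** Overall survival, PFS, ORR and safety do not use this plasma, and the buffy-coat DNA is set aside separately. The sample is a baseline one and allocation is by central IWRS, so a site's choice of unit gives no reason to expect a systematic difference between arms. The scope is consenting patients only, and the visible part of section 9 specifies no plasma DNA analysis.
- **That the pharmacokinetic samples have the same fault.** Appendix VII says "centrifugation will be performed immediately at 3000 rpm", also without a radius. It does not offer two conflicting units, however. PK sampling is confined to selected centres, no effect on any concentration is shown, and section 7.3.1 leaves the bioanalytical method to separate plans that are not available here.

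**Conclusion.** The instruction is wrong as written and should be corrected. For any rotor of 25 cm or less, 2400 rpm delivers at most about two thirds of 2400 g. Over the assumed 10 to 25 cm it delivers 27% to 67%, and below about 20.2 cm it is also weaker than the first spin. Compliant sites can therefore prepare baseline biomarker plasma at different forces, in a step whose stated purpose is to make that plasma fit for DNA analysis.

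The consequence is a risk of residual cells and of a site effect in plasma DNA results among consenting patients. Its size cannot be estimated, because the documents do not say which unit sites used, what rotors they had, or how many cells remained. The conversion is exact; the radius range is an assumption. The point is confined to the biomarker work, and it is worth making because the correction is so cheap.

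**What to change.** 1. In Appendix VIII, step 2, delete the rpm alternative so that the setting is 2400 g for 15 min.
2. Add the conversion, rpm = √(2400 / (1.118 × 10⁻⁵ × r)) with r in cm, or a short table by radius (about 4633, 3783, 3276 and 2930 rpm at 10, 15, 20 and 25 cm).
3. Add one field to the sample log for the force used.
4. Ask sites which setting and rotor they used for plasma already banked. Flag samples spun at 2400 rpm, or at an unknown setting, and repeat any plasma DNA analysis without them as a sensitivity analysis. The synopsis expects recruitment to end in late 2016 or the first quarter of 2017, so much of the plasma may already be stored. The query is best sent while site records and equipment can still be traced.

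Re-spinning thawed plasma is not a remedy: if freezing and thawing has already broken residual cells, a spin meant to pellet cells would not remove the DNA they released.

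The cost is a wording change, a short notice and query to sites, and one log field. No patient gives more blood or makes another visit. The downside is that some banked samples may end up flagged.
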